7.2. Methods for measurement of endpoints for clinical safety

7.2.1.1. Physical examination

A physical examination will be performed at the study center on day -21, 0, 15, 35 and 49. The examination shall be performed by an investigator or the PI who also shall be a medical doctor. The examination is performed as a health screening to make sure participants are eligible to the study according to the inclusion and exclusion criteria. Abnormal findings shall be judged by PI/investigator if clinically significant. Clinically significant abnormal findings discovered at screening shall be documented as medical history and if found after screening these shall be documented as an adverse event.

The physical examination shall include general appearance, auscultation of heart and lungs, abdominal examination, neurological examination and examination of the oral cavity.

7.2.1.2. Blood pressure

Blood pressure will be taken at the study center on day -21, 0, 15, 35 and 49 by an experienced study nurse. It shall be measured as the first parameter during each visit. It should be measured in the left or right arm, in lying position after the subject have been lying down for between 5 to 10 minutes. Blood pressure shall be measured in the identical arm (left or right) at every measurement. Blood pressure is measured using the same kind of calibrated standard equipment for every measurement (Dinamap blood pressure machine). The examination is performed as a health screening to make sure participants are eligible to the study according to the inclusion and exclusion criteria.

7.2.1.3. Electrocardiography (ECG) recording

A 12-lead ECG recording will be performed at screening on day -21 at the study center. It should be measured while the subject is in a supine position. Electrodes are to be placed across the chest according to local routines. ECG is measured using the same kind of calibrated standard equipment for every subject. Each recording should be interpreted by an investigator to scan for eventual abnormalities. The examination is performed as a health screening to make sure participants are eligible to the study according to the inclusion and exclusion criteria.

7.2.1.4. Pregnancy

A pregnancy test will be performed at screening according to the inclusion criteria. If, throughout the study, there is any uncertainty regarding if a participant might be pregnant as judged by study personnel a pregnancy test must be taken. This to evaluate eligibility in the study according to inclusion and exclusion criteria. The pregnancy test will be taken using a high sensitivity urine pregnancy test strip to measure levels of human chorionic gonadotropin (hCG) in a urine sample. The urine sample will be collected and analyzed for urine levels of hCG at the study center. This to determine any eventual pregnancy.

Pregnancy at any time point during the study will lead to withdrawal from the study as soon as the information reaches the investigator, this even if the pregnancy is only temporary due to for example abortion or miscarriage. The subject and the pregnancy should be followed according to procedures described in the safety section in this document.

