4.4.2. Visit 1: Day -21 – Screening

Subjects that pass the pre-screening will be booked to a screening visit at the study center. Potential research subjects will receive both oral and written information about the study plan during the visit. They will have time to ask questions and discuss concerns with an investigator. A written informed consent will be obtained from subjects who want to participate in the study. To get enrolled the potential research subject need to meet all the inclusion criteria and must not meet any of the exclusion criteria. Potential subjects will receive an enrolment number at the screening visit obtained from the electronic Case Report Form. During the visit the subject will receive information about all upcoming visits and study procedures in oral and in written form. All subjects will receive a folder containing all study information needed. Visit 2 will be planned and scheduled.

Visit 2, 3 and 4 will be planned and scheduled.

During the visit the following examinations will be performed:

- Physical examination according to section 7.2.1.1 Physical examination.
- Blood pressure
- Body weight
- Fat mass, water mass and fat free mass will be measured using BIA
- Height measurement for BMI
- Screening blood sample to screen for common diseases that may distort the results and increase the risk of adverse effects. The substances will be measured according to section 7.1.2.6 Blood Samples.
- In fertile female participants human chorionic gonadotropin (hCG) will be measured according to the inclusion and exclusion criteria. hCG will be measured in urine according to section 7.2.1.3. Pregnancy.

All above examinations and samples need to be within normal range (or not clinically significant as judged by PI), according to inclusion and exclusion criteria, for a research subject to be included in the study. Subject will be reminded of the following study visit.

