4.4.4. Visit 3: Day -14 - First DLW measurements

Visiting window: +/- 3 days.

Telephone visit that shall be performed in the afternoon or evening between 17:00 – 22:00 hours. Study personnel will call subjects and repeat the DLW procedure to be performed by the subjects later the same evening. It is crucial that subjects follow the protocol and they shall first be informed on how to collect the first urine sample (sample 1). Secondly, they shall be informed on how to consume the calculated dose of doubly labeled water for the first DLW measurement. The doubly labeled water should be consumed by the subject as the last consumption of the day. The subject will be reminded of visit 3 at the study center in the morning the following day.

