4.4.5. Visit 4: Day -13 – Baseline measurements

Visiting window: Morning visit the day after visit 3.

Study center visit planned in the morning the day after visit 3. The second voiding of the day should be collected at the study center (sample 2) the morning after drinking the doubly labeled water dose. It is important that the first voiding of the day is not collected as sample 2. However, it is not as important if it is the second or third voiding of the day that is collected as sample 2. After sample 2 has been collected body weight shall be measured. Subjects will receive material for collection of urine sample 3-6 at home. Each subject will receive four containers for collection of urine samples and detailed oral and written instructions on how to collect and store the urine samples.

Subjects will receive an accelerometer for measurement of physical activity that will be worn on day -13 to -7. The accelerometer will be attached using a specially designed waist belt and the subject will be instructed how to reattach the device if so to be needed. The subject will be instructed to wear the accelerometer 24 hours per day for seven days. During the meeting a study nurse will attach a portable ECG monitor for a first 24-hour ECG recording. After attachment of the ECG monitor the subject is required to lay down for 1 hour to get a standardized registration, this shall be done at the study center. The subject will then carry the ECG for the following 23-hours during his/her usual activities. The subject will receive two pre-paid envelopes in which the ECG monitor and the accelerometer are to be returned after each registration is completed. Any changes to or new adverse advents will be documented.

During the visit the following examinations will be performed:

Body weight

Study code: ATLAS
Version No: 14.9

Date: 2021-02-01

Fat mass, water mass and fat free mass will be measured using BIA

During the visit on day -13 all future visits and study procedures will be planned and scheduled. The participant will receive dates and times for all upcoming visits in oral and written form.

First measurement with DLW and first ECG registration

Urinary samples will be stored by subject in a home freezer after collection. The containers for collection of urine should be dry and have an airtight lock. They should not be rinsed with water before collection of urine since this can disturb the analysis.

Day -14

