4.4.7. Visit 6: Day 0 – Randomization and start of intervention

Visiting window: +/- 3 hours compared to study visit on day -13. CT- and DXA-scans to be performed +/- 3 days from visit 6 on day 0.

Study center visit where subjects will meet with an investigator and a study nurse. At this visit randomization will take place and intervention will start.

The last urine sample (sample 7) will be collected at the study center in the morning. The subject will return the 4 urinary samples collected from the doubly labeled water measurements at home. The accelerometer used for the basal measurement of physical activity and the ECG equipment is also to be returned if not already sent via prepaid envelope. The subject is required to have had an overnight fast before this visit, this due to the blood sampling. Subjects are to answer the first Dietary Short Questionnaire (SDQ) digitally either using their own mobile phone or a specified computer at the study center.

Any changes to or new adverse advents will be documented.

During the visit the following examinations will be performed:

- Physical examination
- Blood pressure
- Body weight
- Fat mass, water mass and fat free mass will be measured using BIA
- Waist circumference
- Fasting venous blood sampling according to section 7.1.2.6. Blood sampling
- Fasting capillary blood sample for measurement of glucose level according to section 7.1.2.6. Blood sampling

Subjects are included as they are found to be eligible for inclusion in the study. After the baseline period at day 0 subjects will be randomized in a 1:1 ratio into either the intervention group (heavy weight vest) or the control group (light weight vest). Randomization will be through permuted blocks, stratified by age 18-50 years, age 51-65 years and gender performed in the electronic Case Report Form (eCRF) using a built-in function for the purpose. If a subject discontinues their study participation, their randomization code will not be reused, and the subject will not be allowed to reenter the study again.

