4.4.13. Visit 12: Day 35 – End of intervention

Visiting window: +/- 2 days compared to day 0. CT- and DXA-scans to be performed +/- 3 days from visit 12 on day 35.

Subjects will be entitled to another visit with an investigator and a study nurse 5 weeks after the start of intervention. The subject is required to have had an overnight fast before this visit and not have eaten anything before the study visit, this due to the blood sampling. Study subjects will have worn the vests for 8 hours the day before, but they will not wear it during the visit the morning of day 35.

The research subject will be questioned regarding possible adverse events.

The following examinations will be performed:

- Physical examination
- Blood pressure
- Body weight
- Fat mass, water mass and fat free mass will be measured using BIA
- Waist circumference
- Fasting venous blood sampling
- Fasting capillary blood sample for measurement of glucose level

Close to this visit (+/- 3 days) participants will go through a CT- and DXA-scan. Procedures will be performed by experienced personnel operating the CT- and DXA-scan.

The day before visit 13 subjects will receive a text message to their mobile phone with a reminder regarding the fasting blood samples on visit 13.

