5.2. Exclusion criteria

Subjects must not be included in the study if any of the following criteria are fulfilled:

 Chronic disease that could interfere with the participation in the study as judged by the investigator. For example poorly regulated type 1 or type 2 diabetes, cardiovascular disease that effect daily life, pulmonary disease that affects daily life, anemia or malignancy. Study code: ATLAS
Clinical Study Protocol Version No: 14.9
Date: 2021-02-01

2. Chronic pain such as pain that is constant and impairs quality of life as judged by the investigator; for example: significant back, hip and knee pain.

- 3. Regular consumption of medicine or natural supplements that affect weight, inhibit physical activity or increase the risk of adverse effects as judged by the investigator. The following drugs will not be accepted:
 - a. β-blockers, GLP-1-agonists, DPP-IV-inhibitors, SGLT2-inhibitors, sulfonylureas, insulin, orlistat, anti-obesity drugs, antidepressants, bisphosphonates, β2-agonists, oral corticosteroids, diuretics, benzodiazepines, or central nervous system stimulating drugs such as methylphenidate or dextroamphetamine.
 - b. Any illegal drugs according to local laws and regulation
- 4. Gastric by-pass surgery or equivalent metabolic surgery in the gastrointestinal tract.
- 5. Reduced mobility.
- 6. Pregnancy. Females of childbearing potential must confirm to use reliable contraception (intrauterine device, oral contraceptives or condom) and not suspect to be pregnant. Pregnancy test will be taken on all female subjects of fertile age unless permanently sterile, as judged by the investigator. Permanently sterile women can be excluded from the pregnancy test. Permanent sterilization methods include hysterectomy, bilateral salpingectomy and bilateral oophorectomy.
- 7. Change in body weight of 5 kg or greater during the past 3 months or recently started a strict diet. Also, a greater change in body weight than 3 kg difference between day -21 and day 0 will not be accepted.
- 8. Use of any illegal drugs according to local regulations or consuming excessive amounts of alcohol, tobacco, nicotine.
 - a. Excessive amounts of above-mentioned substances defined as:
 - Consumption of more than 9 glasses of wine for women, 14 glasses of wine for men (15 cl/glass 11 % alcohol) or equivalent as judged by the investigator during an ordinary week will not be accepted.

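### The only scheduled pregnancy test is at day -21, nominally 21 and 56 days before the two abdominal CT/DXA sessions, and no test is tied to either session

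*Protocol*

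**What the plan says.** **Testing.** The screening visit (section 4.4.2) contains the one planned test: "In fertile female participants human chorionic gonadotropin (hCG) will be measured according to the inclusion and exclusion criteria". Section 7.2.1.4 confirms the timing: "A pregnancy test will be performed at screening according to the inclusion criteria". It specifies a urine strip, collected and read at the study centre. Any later test depends on suspicion: if at some point "there is any uncertainty regarding if a participant might be pregnant as judged by study personnel a pregnancy test must be taken". The examination lists for days 0, 15, 28, 35 and 49 (4.4.7, 4.4.10 and 4.4.12 to 4.4.14) contain no pregnancy test. The study-plan table in 4.2 has no row for one either, but it also omits the screening strip, so its silence adds little.

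**Scans.** Sections 4.4.7 and 4.4.13 place CT and DXA within 3 days of visit 6 (day 0) and of visit 12 (day 35). For the second session the text reads "CT- and DXA-scans to be performed +/- 3 days from visit 12 on day 35". Section 2.3 acknowledges that both procedures give a small radiation dose and does not mention pregnancy there. It also says that subjects gain no direct benefit.

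**Other safeguards.** Section 5.2 states: "Females of childbearing potential must confirm to use reliable contraception (intrauterine device, oral contraceptives or condom) and not suspect to be pregnant". Section 5.5 requires the exclusion criteria to remain unmet throughout, and 7.2.1.1 has a doctor examine subjects on days 0 and 35, among others. A known pregnancy leads to withdrawal.

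**Pregnancy follow-up.** Section 8.5 describes the vest as low risk, judges the malformation risk very low, and on that basis follows a pregnancy to the end of the study and not necessarily to birth. The investigator reviews any pregnancy still ongoing then. Radiation is not mentioned.

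**The concern.** Both radiation sessions come weeks after the only planned test. A woman who conceives around or after screening, and whom nobody suspects of being pregnant, can reach one or both sessions without the protocol calling for a strip. The scans are research measurements in a trial that states no direct benefit to participants, so an avoidable exposure has nothing to set against it. The trial already uses the tool that would often prevent it.

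The matter concerns participant safety. The primary endpoint, the sample size and the comparison of the arms do not depend on it.

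**Working it through.** The protocol gives no test-to-scan interval, so there is no figure to reproduce. The intervals follow from the visit schedule.

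**Inputs**
- Test: visit 1, day -21, with no window stated (4.4.2).
- Visit 3, day -14: "Visiting window: +/- 3 days" (4.4.4).
- Visit 4, day -13: "Visiting window: Morning visit the day after visit 3" (4.4.5), so it moves with visit 3.
- Visit 6, day 0: "Visiting window: +/- 3 hours compared to study visit on day -13" (4.4.7), so day 0 moves with visit 4.
- First scans: within 3 days of visit 6 (4.4.7).
- Visit 12: day 35, plus or minus 2 days, with scans within 3 days of the visit (4.4.13). The methods sections are narrower for the second session: day 35 plus or minus 2 days for DXA (7.1.2.2) and plus or minus 3 days for CT (7.1.2.3).

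**Formula.** Age of the test = scan day - (-21).

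**Nominal.** First session: 0 + 21 = 21 days. Second session: 35 + 21 = 56 days.

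**Carry-through of the visit 3 window.** Visit 3 at its latest is day -14 + 3 = -11. Visit 4 is then day -10, and visit 6 falls 3 days late relative to screening.

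| Upper limit | Day 0 on time | Day 0 three days late |
|---|---|---|
| First session (4.4.7) | 21 + 3 = 24 | 24 + 3 = 27 |
| Second session, 4.4.13 | 21 + 35 + 2 + 3 = 61 | 61 + 3 = 64 |
| Second CT, 7.1.2.3 | 21 + 35 + 3 = 59 | 59 + 3 = 62 |
| Second DXA, 7.1.2.2 | 21 + 35 + 2 = 58 | 58 + 3 = 61 |

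**Lower limit.** The same windows can shorten the intervals: 21 - 3 - 3 = 15 days for the first session and 56 - 3 - 2 - 3 = 48 days for the second (4.4.13 windows).

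**Do the safeguards trigger a test without suspicion?**
- Contraception is confirmed by the woman herself, and a condom alone qualifies.
- The rule that exclusion criteria stay unmet has no scheduled test behind it for pregnancy.
- The examination in 7.2.1.1 covers general appearance, heart and lungs, abdomen, neurology and the oral cavity. It would not reliably reveal an early pregnancy.
- The for-cause test is mandatory once staff are uncertain, but no visit list prompts them to ask.

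None of these guarantees a test before a scan. A pregnancy that began around screening would be about 56 / 7 = 8 weeks past conception at the nominal second session. A strip would be expected to detect it by then, and the protocol would still not require one.

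**The case against.** The strongest reply is that the protocol already has a layered scheme: required contraception, eligibility that must hold throughout, regular contact with staff, a mandatory test at any doubt, and withdrawal once pregnancy is known. On this view, the point is only a preference for routine over for-cause testing. The safeguards are real and lower the risk, and this is a reason to rate the point minor. They do not close the gap, because each rests on self-report or on somebody suspecting pregnancy.

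A second reply is that the scan sites may check for themselves. CT is done in a hospital radiology department, DXA follows local routines (7.1.2.2), and working manuals are promised in 10.1. None of these is shown. A reader might infer that women are scanned unchecked, but the document does not support this; it shows only that the protocol requires no check. Research-only radiation should still not depend on an unstated routine.

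Third, a reader might take 64 days as the limit for the second session. It is the limit only under 4.4.13. Sections 7.1.2.2 and 7.1.2.3 give 61 days for DXA and 62 for CT. The intervals can also be shorter than nominal, and none of them measures risk.

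Finally, one might read 8.5 as cutting off follow-up of an exposed pregnancy. It does not: the investigator reviews any ongoing pregnancy and may extend follow-up. The malformation sentence is also not expressly confined to the vest. What remains is that the review has no prompt to consider CT/DXA exposure.

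**Conclusion.** The point stands as a minor safety gap with a cheap remedy. The only scheduled test is 21 and 56 days old at the nominal sessions. At the window limits it is up to 27 days old at the first and 61 to 64 days old at the second. The upper figures assume that the visit 3 window carries through visits 4 and 6 to day 0.

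The harm cannot be sized. The document gives no number of women of childbearing potential, no pregnancy rate and no fetal dose, and it calls the dose small. The event is probably rare. Confidence is medium, because an unseen radiology routine might already close the gap in practice. The omission in 8.5 is a secondary matter of wording.

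**What to change.** **Testing.** In 7.2.1.4 and in the lists for visits 6 and 12, require a negative urine hCG strip in women of childbearing potential before each CT/DXA session, on the scan day where feasible.
- On day 0, read it before randomization and before scanning. This also avoids randomizing a woman who would then have to be withdrawn. The remainder of urine sample 7, which 4.5.3 otherwise destroys, will serve if that sample is collected at the study centre. The Figure 4 legend in 4.1 also allows collection at home, and a fresh void is then needed.
- A scan on another day, which the windows allow before or after the visit, needs its own strip. Because 7.2.1.4 now fixes reading at the study centre, add one clause that permits reading at the scan site.

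**Section 8.5.** Name CT/DXA exposure as a factor in the investigator's review of an ongoing pregnancy.

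**Cost.** Two strips per woman if CT and DXA share a day, and up to four otherwise. Section 9.3 implies about 130 × 0.5 = 65 enrolled subjects. Even if all were women of childbearing potential, that is 65 × 2 = 130 to 65 × 4 = 260 strips. The downsides are minor logistics when scans fall on separate days or sites and an occasional withdrawal before a scan. Very early pregnancies can still be missed.

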7.2.1.5. Illness or symptoms related to infectious diseases

All participants will be instructed only to attend physical visits at the study center if feeling healthy and if they are without any symptoms related to any infectious diseases. In case of illness or symptom/symptoms related to infectious diseases such as fever with a body temperature of > 37,5° C, shivering, sore throat, cough, headache or general muscle pain participants are instructed

Study code: ATLAS

Version No: 14.9

Date: 2021-02-01

to stay at home. Participants will be reminded to follow these rules upon all study visits. Body temperature is checked on every physical visit at Clinical Trial Center, Gothia Forum.

With regards to the current covid-19 pandemic study participants and study personnel are obliged to follow current national and local guidelines in Sweden and Västra Götalandsregionen, this also regarding to when it is appropriate to visit the study center. For example, these recommendations include to follow the recommended time-periods for how long a participant need to have been without symptoms before visiting the study center, how to manage if someone near the participant is ill or have been confirmed having covid-19. It is a risk for both the subject and the study personnel to get infected with covid-19 at physical visits. To minimize the risks of spreading the infection all study personnel are to follow local guidelines to use appropriate protection clothing which, if recommended, include a visor, gloves and a face mask.

If appropriate, a subject with symptoms of covid-19 may be offered an acute Polymerase Chain Reaction (PCR) test for covid-19 to conclude if the symptoms are caused by covid-19. Testing will then be according to local routines at Sahlgrenska University Hospital. This test may be offered if a negative result makes it possible to attend a physical visit at the study center within the visiting window. A positive PCR test for covid-19 will lead to exclusion of the subject from the study. Applicability of testing will be judged by the investigator. If no acute test is applicable, subjects will be encouraged to visit its own local primary care center for testing according to local guidelines.

